7.1. INFORMED CONSENT

- Informed consent of participants, or legal tutor representative in the case of minors, is required prior to inclusion in the study and at the moment of the study extension for the primary school children; see the appendix 'Information and consent form'.
- Informed assent: The children will receive age-appropriate information on the study and may refuse to be included in the study. A new informed assent is provided prior to testing period 4 for primary school children.

7.2. POTENTIAL RISKS

- Biological sample (saliva swap) risks are minimal.
- Information of the result can be considered to be psychologically or socially difficult to manage in the current context of a pandemic. The medical staff performing this study will give appropriate advice.

7.3. POTENTIAL DIRECT BENEFITS FOR PARTICIPANTS AND INDIRECT BENEFITS FOR BROADER SOCIETY

The potential benefits are mainly indirect as the data collected will help improve and guide efforts to understand the SARS-CoV-2 pandemic and partially the transmission dynamics in the paediatric population and among school staff. Participants will also receive the test results, unless they do not wish to receive these.

7.4. CONFIDENTIALITY

Participant confidentiality will be maintained throughout the investigation. Two different databases will be created. One will contain identifying data such as names, surnames, telephone numbers, e-mail addresses and a unique registration code assigned to each participant. The other database will contain the study data (laboratory results and questionnaire information) and will have as identifier the unique registration code. These 2 databases will be kept separately and will be protected by a password. If the investigator entrusts the data for statistical processing, only the second database will be entrusted to this third person. As such, data in the database for analysis will be pseudonymised. Only the principal investigator will keep the database containing personal information and the unique registration code (identification number) assigned to each participant/child.

7.5. BIOLOGICAL SPECIMEN

The biological specimen will be stored after entering the biobank (located at Sciensano) for a duration of maximum 10 years after which they will be destroyed. Specimens might be used for additional COVID-19 related testing. If the participant wishes its biological specimen to be destroyed upon completion of the study, this will need to be mentioned in the informed consent form.

7.6. STUDY INSURANCE

We have an insurance for this study with Ethias. Insurance reference is: 45.437.023

An ethical committee review has been sought for this protocol from the Ethics Committee Research of UZ Gent and ethics approval was received2021. Ethical committee clearance: B.U.N.: B6702020000744.

7.7. DATA PROCESSING AND PROTECTION (GDPR)

Data processing and protection for this study complies with the provisions of the regulations for the protection of Personal Data, including but not limited to the EU General Data Protection Regulation 2016/679 of 27 April 2016 and its implementing decrees. Questions and other issues regarding data protection will be addressed to Sciensano Data Protection Officer, e-mail address: [contact].

The General Data Protection Regulation (GDPR, the European legislation governing the protection of personal data, applies to this study. The legal basis on which the data are processed is consent.

- See Article 6 § 1 (a) of the GDPR
- See Article 9 § 2 (a) of the GDPR

7.8. DISTRIBUTION OF RESULTS

The study protocol will be registered at [Clinicaltrials.gov](https://clinicaltrials.gov).

Anonymous study results should be made accessible and available as soon as possible after every testing period and at the end of the study to public health authorities involved in management of the COVID-19 epidemic in Belgium. This can be done through a policy brief or presentation. Sciensano will coordinate the distribution of results. These results will be also published on the relevant websites of these institutions.

The general public will also be informed regarding these anonymous results through press communications. This will be done by the communication departments of Sciensano and of the study partners.

Scientific peer-reviewed publications (possible short publication, regular paper) will be prepared to add to the body of evidence and availability for the global scientific community and public health decision makers.

Appendices

a. Questionnaires:

- Parents: 1ste contact,
- Parents: 2nd and 3rd contact,
- Schools: baseline
- Schools: 2nd and 3rd testing period
- Parent registration form
- School staff registration form
- School staff: baseline
- School staff: 2nd and 3rd testing period

b. Additional questions to be added at questionnaire for parents at 4th and 5th testing period

1. Werd uw kind gevaccineerd tegen het coronavirus (COVID-19)?

- Ja, mijn kind kreeg één dosis van een vaccin
- Ja, mijn kind kreeg twee dosissen van een vaccin
- Neen, mijn kind kreeg nog geen vaccin

1.1. Indien optie 1: Datum van de eerste dosis:

1.2. Indien optie 2: Datum van de tweede dosis:

Indien u de exacte datum van de vaccinatie niet kent, kan u aangeven wanneer uw kind ongeveer werd gevaccineerd.

1.3. Met welk vaccin werd uw kind gevaccineerd ?

- Ik weet het niet
- Het Pfizer-BioNTech (Comirnaty) vaccin
- Het Moderna vaccin
- Het AstraZeneca (Vaxzevria) vaccin
- Het Johnson & Johnson (Janssen) vaccin
- Een ander vaccin, namelijk:

1. Votre enfant a-t-il été vacciné contre le coronavirus (COVID-19)?

- Oui, mon enfant a reçu une première dose d'un vaccin.
- Oui, mon enfant a reçu deux doses d'un vaccin.
- Non, mon enfant n'a pas encore été vacciné

1.1. En cas d'option 1: Date de la première dose:

1.2. En cas d'option 2: Date de la deuxième dose:

Si vous ne connaissez pas la date exacte de la vaccination de votre enfant, vous pouvez indiquer une date approximative.

1.3. Avec quel vaccin votre enfant a-t-il été vacciné?

- Je ne sais pas
- Vaccin de Pfizer-BioNTech (Comirnaty)
- Vaccin de Moderna
- Vaccin d'AstraZeneca (Vaxzevria)
- Vaccin de Johnson & Johnson (Janssen)
- Un autre vaccin, notamment:

2. Zijn de volwassenen (personen van 18 jaar en ouder) die onder hetzelfde dak wonen als uw kind gevaccineerd tegen COVID-19?

- Ja, iedereen is gevaccineerd
- Sommige zijn gevaccineerd, sommige niet
- Nee, niemand is gevaccineerd.
- Ik wens deze vraag niet te beantwoorden.

2.1. Indien antwoordmogelijkheid 1:

Is iedereen volledig gevaccineerd* tegen COVID-19?

- Ja
- Neen

(Volledige vaccinatie* = één dosis van het Johnson & Johnson vaccin ; twee dosissen van een ander vaccins)

2. Est-ce que les adultes (18 ans et plus) vivant sous le même toit que votre enfant sont vaccinés contre la COVID-19 ?

- Oui, tout le monde est vaccinés
- Certains le sont vaccinés, d'autres ne le sont pas.
- Non, personne n'est vacciné.
- Je ne souhaite pas répondre à cette question.

2.1. Si option 1 :

Est-ce que tout le monde est complètement vaccinés* contre la COVID-19 ?

- Oui
- Non

(Vaccination complète* = une dose pour le vaccin Johnson & Johnson ; deux doses pour un autre vaccin)

- c. Informed consent form child (to be signed by parent/legal caregiver) and age appropriate informed assent forms for first part of the study (December 2020 – June 2021)
- d. Informed consent and assent forms for study extension to be completed prior to testing period 4.
- e. Informed consent form school staff

References

1. COVID-19 Map [Internet]. Johns Hopkins Coronavirus Resource Center. [cited 2020 Sep 3]. Available from: <https://coronavirus.jhu.edu/map.html>
2. Epistat – COVID-19 Belgian Dashboard [Internet]. [cited 2020 Sep 3]. Available from: <https://epistat.wiv-isp.be/covid/covid-19.html>
3. Ludvigsson JF. Children are unlikely to be the main drivers of the COVID-19 pandemic - A systematic review. *Acta Paediatr Oslo Nor* 1992. 2020;109(8):1525–30.

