PREVALENCE AND INCIDENCE OF ANTIBODIES AGAINST SARS-COV-2 IN CHILDREN AND SCHOOL STAFF MEASURED FOR ONE YEAR IN BELGIUM: A SERO-EPIDEMIOLOGICAL PROSPECTIVE COHORT STUDY – AMENDED PROTOCOL

July 2021

Summary

This protocol amendment describes changes in:

1. Main objective
2. Secondary objectives
3. Study population
4. Questionnaire
5. Testing periods of participants

The **table of changes**, with rationale, the amended protocol, the questions added to the questionnaire and informed consent forms are provided in the following pages. **The sections that have been changed are highlighted in yellow.**

Table of changes

Changes July 2021:

Change / addition	Rational	Affected protocol section

Testing periods: Extension of the study period from 1/9/2021 tot 31/3/2022 with addition of two testing periods (September 2021 and December 2021)
	
The pandemic has not been fully controlled and new waves remain possible. The evolution of the pandemic remains unclear, with the circulation of new variants of concern, a still ongoing vaccination campaign and, so far, no vaccine availability for the paediatric population. With the start of the new school year no vaccine will yet be licensed for use in the under 12 year olds, resulting in primary school children remaining a SARS-CoV-2 infection susceptible population while it is unclear how this will be impacted by a (partially) vaccinated adult population.
 
Further surveillance of the seroprevalence in the paediatric population will inform us on the proportion of children with prior infection. Vaccination in the adult population renders further follow-up of school staff less useful. Similarly, the higher likelihood of vaccination among secondary school pupils making further follow-up of this group also less useful.
 
Keeping the same primary school study population, which is selected to be representative for primary school children of 8-9 year old in Belgium, will enable us to continue providing Belgian paediatric estimates and having a one year cohort including the same children over time. This allows us to provide both seroprevalence point-prevalence estimates and follow changes in incidence. Additionally, we will be able to get more insight in waning immunity and how this is captured by diagnostic tools.
	
3. Methods 3.2. Study design 3.6. Data collection 3.6.1. Data collection procedure 7.6. Study insurance

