3.2. STUDY DESIGN

This study will be set up as a prospective cohort study.

Children and school staff will be recruited at the 1st testing period in the participating school. Samples will be taken within a timeframe of maximum 4 weeks for all the participants.

Parents/legal child caregiver and staff will need to complete a questionnaire at each of the testing moments providing basic socio-demographic characteristics (at baseline only) and risk-behaviour and health characteristics including presence of symptoms during the time since the previous testing period (at each of the testing periods). The questionnaire will be completed ~~by a parent of caregiver~~ through a secured online application during the same week as the collection of a saliva sample. ~~from the child.~~

The study will last 12 months. There will be in total 3 testing periods when data and sample collection will be performed for the total study population; in ~~October~~ December 2020 (Baseline), ~~January~~ February 2021 (M3) and April/May 2021 (M6). There will be a 4th and 5th testing period for primary school pupils only: in September 2021 (M9) and December 2021 (M12).

Saliva samples will be sent to the Sciensano laboratory for analysis. Serological test results will be communicated to the child's parent/legal caregiver by a closed letter through the participating school.

Epidemiological data analysis will be performed and reported after each testing period and at the end of the study.

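### Adult household vaccination is recorded without dates, so it cannot be ordered against a child's infection before September 2021

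*Combined protocol and SAP*

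**What the plan says.** Appendix b introduces the new items as "Additional questions to be added at questionnaire for parents at 4th and 5th testing period". Section 3.2 puts these periods in September and December 2021.

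- **Adults (item 2).** The Dutch form asks whether adults "die onder hetzelfde dak wonen als uw kind gevaccineerd tegen COVID-19". The French form asks "Est-ce que les adultes (18 ans et plus) vivant sous le même toit que votre enfant sont vaccinés contre la COVID-19". The answers are everyone, some, nobody, or no wish to answer. Neither version has a date field. The one follow-up, item 2.1, goes only to households answering everyone. It asks whether vaccination is complete, defined by doses: "Volledige vaccinatie* = één dosis van het Johnson & Johnson vaccin ; twee dosissen van een ander vaccins".
- **Child (item 1).** The date is requested: "1.1. Indien optie 1: Datum van de eerste dosis" after one dose, "1.2. Indien optie 2: Datum van de tweede dosis" after two. An approximate date is accepted.
- **Reason for the extension.** The July 2021 table of changes says that primary pupils enter the new school year susceptible and that "it is unclear how this will be impacted by a (partially) vaccinated adult population". It also says that the vaccination campaign was still running.
- **Analysis.** No objective, outcome or analysis names household vaccination. The nearest is the secondary objective on risk factors among children (section 2). Section 3.7 analyses it by Poisson regression on sero-positivity and does not say when an exposure must precede the outcome. Section 3.7 also lists incidence rates that leave out participants who were non-susceptible at the prior survey.

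**The concern.** Sero-positivity in September 2021 can reflect an infection at any earlier time. Seroconversion between periods 3 and 4 can reflect one at any time from April/May to September. The household item describes only the day the form is completed, at the end of that window. A home whose adults completed vaccination in August is coded as vaccinated even if the child was infected in May.

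If the timing of adult vaccination is unrelated to the child's infection, this dilutes any protective association. If an infection in the home delayed or prompted vaccination, the bias could go either way; the documents give no information on that.

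Results are to reach public health authorities after every testing period (section 7.8). A diluted association could be read as adult vaccination doing little for children at home. The dates cannot be rebuilt later from the form as written.

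**Working it through.** **1. The plan's own figure.** The documents give no figure for an effect of household vaccination. The only relevant one is the sample size in section 3.3, and it reproduces. The margin of error is 1.96 × √(0.06 × 0.94 / 400) = 2.3%. The cluster size is 400 × 2 / 41 = 19.51, rounded up to 20, and 20 × 41 = 820. With the design effect of 2, 820 children count as 410. The point does not depend on these figures, except for the power illustration in step 4.

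**2. Dilution formula.** Let RR be the true relative risk in vaccinated time. Among children in homes coded vaccinated, let f be the share of infections, counted at the unvaccinated rate, that fell before the adults were vaccinated. Then

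observed RR = f + (1 − f) × RR.

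The documents give neither RR nor f, so both are assumed and varied. Under constant risk:

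- Half of the vaccinated homes complete before the interval and half at its middle: f = 0.25, and 0.5 × 0.50 + 0.5 × 0.75 = 0.625.
- All complete at the middle: f = 0.50, and 0.5 × 1 + 0.5 × 0.50 = 0.75.

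| True RR | f = 0 | f = 0.25 | f = 0.50 | f = 0.75 |
|---|---|---|---|---|
| 0.30 | 0.30 | 0.475 | 0.65 | 0.825 |
| 0.50 | 0.50 | 0.625 | 0.75 | 0.875 |
| 0.70 | 0.70 | 0.775 | 0.85 | 0.925 |

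**3. Where each outcome falls.**

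- *Seroconversion, periods 3 to 4.* Status is read at the end of the interval, so the dilution applies.
- *Sero-positivity at period 4 or 5.* This also counts infections before period 3, so f can be larger. The item is first asked at M9 of a 12-month study.
- *Seroconversion, periods 4 to 5.* Period 4 status comes first, so f = 0 for homes already vaccinated. What remains is that a share s of the reference homes may be vaccinated during the interval, say at its middle. The observed RR is RR / [1 − s + s × (0.5 + 0.5 × RR)]. With RR = 0.50, s = 0.05 gives 0.50 / 0.9875 = 0.51, and s = 0.20 gives 0.50 / 0.95 = 0.53.

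**4. Effect on power, one assumed scenario.** Take an effective n of 410, 75% of homes vaccinated, 20% risk in the unvaccinated group, a true RR of 0.50, and a two-sided 5% comparison of two proportions. Power is 73% at f = 0, 47% at f = 0.25, 23% at f = 0.50 and 9% at f = 0.75.

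**5. Does status at the start of the interval suffice for periods 3 to 4?** Not fully. Adults vaccinated during the interval would then sit in the reference group. With a true RR of 0.50:

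- Half of the reference homes vaccinated at the middle: 0.50 / (0.5 × 1 + 0.5 × 0.75) = 0.50 / 0.875 = 0.57.
- All of them: 0.50 / 0.75 = 0.67.

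Homes vaccinated during the interval therefore need a category of their own.

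**The case against.** The strongest reply is that the form already serves the question behind the extension. The table of changes speaks of the new school year, which is the interval from September to December 2021. The item is asked at period 4, before that interval, and again at period 5. A reader might infer that the missing date leaves the effect of adult vaccination in the new school year misclassified. The documents do not support that: step 3 puts the remaining bias there at 0.50 becoming about 0.51 to 0.53. What does stand is that the plan nowhere says the period 4 answer will be used in this way.

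Second, household vaccination is not a stated objective, and the rationale speaks of the adult population rather than the adults in the child's home. This is correct and limits the weight of the point. It remains a natural candidate under the risk-factor objective, and the item was added in the same amendment.

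Third, a vaccination date cannot by itself order an infection that serology places only between two samples. This also stands. It is why splitting the April/May to September interval at the vaccination month would not work, and why the outcome must change as well as the form.

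Fourth, households answering some are not asked item 2.1. They can be analysed as a partial category, so this loses detail but is not a timing error.

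Finally, the base questionnaires in Appendix a are listed but not shown. An earlier dated item on adults cannot be excluded, although the table of changes presents the vaccination questions as additions.

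**Conclusion.** The point holds for two uses of the item: with sero-positivity at period 4 or 5 as outcome, and with seroconversion between periods 3 and 4. In both, undated status lets vaccination that followed the infection count as exposure. The likely result is attenuation, illustratively from 0.50 to between 0.63 and 0.75, and more if many of the counted infections are old. These sizes rest wholly on an assumed relative risk, assumed timing of adult vaccination and constant risk. The direction also assumes that an infection did not itself change when the adults were vaccinated.

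Seroconversion between periods 4 and 5 is largely sound if period 4 status is used as the exposure. A reader should not infer that the study's seroprevalence estimates are affected: the primary objective is descriptive and does not use this item. The change is worth making because it is cheap and the missing timing cannot be recovered later.

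**What to change.** 1. **Form.** In Appendix b item 2, add the approximate month in which the first and the last adult in the household completed vaccination, allowing an estimate as item 1 does. Asking item 2.1 after the answer some is optional.
2. **Outcome.** In section 3.7, relate household vaccination to seroconversion since the previous sample among children negative at that sample, not to prevalent sero-positivity. This fits the incidence measure already listed there.
3. **Exposure, periods 4 to 5.** State that the period 4 answer is the exposure.
4. **Exposure, periods 3 to 4.** Use the reported month to class households as vaccinated before the interval, during it, or not by its end. Alternatively, use the fraction of the interval vaccinated.

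The cost is one or two items in an online form that is already being amended, with approximate recall of months. Children without a negative previous sample leave this analysis. Pupils newly recruited for the extension, having no period 3 sample, can contribute only to the interval from period 4 to period 5.
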